#### 5.1.2. *Multicentre Studies*

Due to this being a safety and tolerability study with low patient numbers per dose there is no plan to fit centre as a covariate in any of the models. The demographic/disposition listings will make it clear which sites each patient were attributed to.

#### 5.1.3. *Multiple Comparisons/Multiplicity*

No adjustments will be made for multiplicity.

## 5.2. Patient Disposition

A detailed description of patient disposition will be provided at the end of the study. All patients who discontinue from the study will be identified, and the extent of their participation in the study will be reported. If known, a reason for their discontinuation will be given.

### 5.2.1. Patient Characteristics

The patient's age, sex, race, weight, height, APOE4 status or other demographic characteristics will be recorded and may be used in the PK, PD, and safety analyses as quantitative or classification variables. These characteristics will be listed and summarised at baseline, with the exception of weight which will also be summarised over time.

## 5.3. Protocol deviations

All clinically relevant programmable protocol deviations will be listed by pre-determined categories (e.g., inclusion/exclusion criteria, non-compliance with protocol procedures, use of excluded treatments, informed consent/assent process, continuing after meeting withdrawal criteria, or other). The following protocol deviations relevant to this study have been identified in [Table LMDD.1](#).

**Table LMDD.1. Description of Programmable Protocol Deviations**

Category	Source	Methods of Identification
Category: Informed Consent		
Informed Consent Not Obtained/Missing/Late	Programmable (clinical database)	Compare all assessment dates to ICD date (except those assessments that may occur before ICD, e.g., disease assessments) from SDTM datasets
Category: Eligibility		
Participation of a subject(s) that did not meet study inclusion/exclusion criteria	Mixed (Monitoring and clinical database)	Review of the following programmable and relevant protocol inclusion/exclusions criteria: [1] CDR, FSCRT, MMSE and amyloid, [3] Age [4] BMI [29]C- SSRS [35] stable concomitant medications.
Discontinuation due to protocol violation during the study	Mixed (Monitoring and clinical database)	Review of reasons for discontinuation
Category: Study Procedures		
Excluded concomitant medications	Mixed (Monitoring and clinical)	Study specific definition: a list with all concomitant medication will be generated, and CRP will flag those

	database)	excluded (the flagged medications will be used in programming to flag important protocol deviations)
--	-----------	--

Abbreviations: CRP = clinical research physician; ICD = informed consent document.

### **5.3.1. Japanese and non-Japanese Patients**

In addition to combined summaries selected TFLs will be reproduced in triplicate for Japanese and non-Japanese subjects (All subjects, Japanese only subjects and Non-Japanese only subjects.). These will include demography and baseline characteristics, AE summaries, frequency of increases in QTc intervals (greater than 30msec and greater than 60msec) and maximum QTc values exceeding 450msec, 480msec and 500msec. If differences are observed between Japanese and non-Japanese then further analyses and/or split summaries maybe produced.

### **5.3.2. Subgroup Analyses**

Any subgroup analyses will be exploratory (posthoc) in nature.

### **5.3.3. Concomitant Therapy**

Concomitant medication will be coded using the WHO drug dictionary. Concomitant medications will be listed and summarised by treatment.

### **5.3.4. Extent of Exposure**

Dosing information for each individual subject will be listed.

## **5.4. Safety Analyses**

Safety parameters that will be assessed include AEs, MRI, safety laboratory parameters, vital signs, and ECG parameters. The parameters will be listed and summarised using standard descriptive statistics for values at each time point as well as changes from baseline. A listing of all patients' lab values and a listing of abnormal lab values (for that parameter) during the treatment period will be provided and results will be summarised. Outliers will also be identified and listed where appropriate. Additional analyses may be performed if warranted upon review of the data.

### **5.4.1. Adverse Events**

All investigational product and protocol procedure AEs will be listed, and if the frequency of events allows, safety data will be summarized using descriptive methodology.

The incidence of symptoms for each treatment will be presented by severity and by association with IP as perceived by the investigator. Symptoms reported to occur prior to randomization will be distinguished from those reported as new or increased in severity during the study. Each

symptom will be classified by the most suitable term from the medical regulatory dictionary. The number of IP-related SAEs will be reported.

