2.2. MAD Treatment Period (Visits 2 to 19)

Study Schedule Protocol I8G-MC-LMDD

MAD Treatment Period (Visits 2 through 19)

| Visit | V2 ^a Rand | V3 | V4 | V5 | V6 | V7 | V8 | V9 | V10 | V11 | V12 | V13 | V14 | V15 | V16 | V17 | V18 | V19 |
|--|-------------------------|----------------|------|----|----|----|-----------------|-----------------|-----------------|------------------|------------------|------------------|------------------|------------------|------------------|------------------|------------------|------------------|
| Day Relative to First Dose | -8 | 1 ^b | 2 | 4 | 8 | 15 | 29 ^b | 57 ^b | 85 ^b | 113 ^b | 141 ^b | 169 ^b | 197 ^b | 225 ^b | 253 ^b | 281 ^b | 309 ^b | 337 ^b |
| Week | | 1 | 1 | 1 | 2 | 3 | 5 | 9 | 13 | 17 | 21 | 25 | 29 | 33 | 37 | 41 | 45 | 49 |
| Tolerance Interval for Visit (days) | ±7 ^a | 0 | +4 h | ±1 | ±1 | ±1 | ±4 | ±4 | ±7 | ±7 | ±7 | ±7 | ±7 | ±7 | ±7 | ±7 | ±7 | ±7 |
| Dosing | | | | | | | | | | | | | | | | | | |
| Study medication administered | | D1 | | | | | D2 | D3 | D4 | D5 | D6 | D7 | D8 | D9 | D10 | D11 | D12 | D13 |
| Administrative Procedures | | | | | | | | | | | | | | | | | | |
| Body weight | X | | | | | | | | | | | 0 | | | | | | 0 |
| Previous/concomitant medications | X | X | X | X | X | X | X | X | X | X | X | X | X | X | X | X | X | X |
| Inclusion/exclusion review | X | | | | | | | | | | | | | | | | | |
| Preexisting conditions/AEs | | X | X | X | X | X | X | X | X | X | X | X | X | X | X | X | X | X |
| Cognitive Assessments and Functional Scales^{c,d} | | | | | | | | | | | | | | | | | | |
| ADAS-Cog ₁₄ | X | | | | | | | | | | | | X | | | | | |
| ADCS-MCI-ADL24 | X | | | | | | | | | | | | X | | | | | |
| MMSE | X | | | | | | | | | | | | X | | | | | |
| NTB | X | | | | | | | | | | | | X | | | | | |
| dCDT | X | | | | | | X | X | X | X | X | X | X | X | X | X | X | |
| Safety Assessments | | | | | | | | | | | | | | | | | | |
| Vital signs | X | 0, 0.5, 2 | 24 | 72 | X | X | 0, 0.5, 2 | 0, 0.5, 2 | 0, 0.5, 2 | 0, 0.5, 2 | 0, 0.5, 2 | 0, 0.5, 2 | 0, 0.5, 2 | 0, 0.5, 2 | 0, 0.5, 2 | 0, 0.5, 2 | 0, 0.5, 2 | |
| C-SSRS/SHSF | X | 0 | X | X | X | X | 0 | 0 | 0 | 0 | 0 | 0 | 0 | 0 | 0 | 0 | 0 | 0 |
| Physical examination | | 0 | | | X | | | 0 | 0 | 0 | 0 | 0 | 0 | 0 | 0 | 0 | 0 | 0 |
| Neurological examination | | 0 | 24 | | X | X | 0 | 0 | 0 | 0 | 0 | 0 | 0 | 0 | 0 | 0 | 0 | 0 |

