- h The flortaucipir F 18 PET scan should be conducted at Visit 13 should the patient follow the 25-week treatment regimen or at Visit 19 for the 49-week treatment regimen. The flortaucipir F 18 PET scan should be completed at Visit 20 if the patient discontinues treatment after Visit 13 and before Visit 19. Patients permanently discontinued from study treatment due to initiation of a prohibited medication known to prolong the QT-interval should not have an ED flortaucipir F 18 scan unless the scan can be performed prior to initiation of the prohibited medication. Patients who have continued on study after introduction of a drug known to prolong QT interval (with sponsor approval) need a minimum of 14 days or 5 half-lives, whichever is longer, without that drug prior to the flortaucipir scan.
- i The baseline V2 LP will be performed no closer than 24 hours before first dose. Dosing may not proceed until patient has been at least 12 hours free of symptoms of post-LP headache, if present. Refer to Section 9.5.1 for details of sampling.
- j Coagulation test results should be reviewed before each LP. Concomitant medications should be reviewed to ensure that no changes to anticoagulation or antiplatelet therapy have occurred since the last coagulation test.
- k LPs are scheduled at either Visits 13, 19, 20, or early discontinuation. The corresponding coagulation test is required up to 2 weeks prior to the next scheduled LP.
- l The LP should be conducted at Visit 13 should the patient follow the 25-week treatment regimen or at Visit 19 for the 49-week treatment regimen. The LP should be completed at Visit 20 if the patient discontinues treatment after Visit 13 and before Visit 19.

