Abbreviations: ADAS-Cog₁₄ = 14-item Alzheimer's Disease Assessment Scale – Cognition; ADCS-MCI-ADL24 = 24-question Alzheimer's Disease Cooperative Study/Activities of Daily Living scale adapted for MCI patients; AE = adverse event; CRF = case report form; C-SSRS = Columbia-Suicide Severity Rating Scale; D = dose; dCDT = digital clock drawing test; ECG = electrocardiogram; ED = early discontinuation; EDTA = ethylene diamine tetraacetic acid; IV = intravenous; LP = lumbar puncture; MAD = multiple ascending dose; MMSE = Mini-Mental State Examination; MRI = magnetic resonance imaging; NTB = Neuropsychological Test Battery; PD = pharmacodynamics; PET = positron emission tomography; PK = pharmacokinetics; rand = randomisation; RNA = ribonucleic acid; SC = subcutaneous; SHSF = Self-Harm Supplement Form.

Notes:

- (i) Patients who have completed at least the 25-week treatment period will be followed up for 16 weeks after completion of dosing (Visits 20 to 24) as per the Schedule of Activities.
- (ii) Pharmacokinetic time points indicated as zero (0) denote trough samples immediately prior to study drug infusions/injections. Other assessments denoted as “0” will be collected prior to study drug infusions/injections. Samples listed as non-zero numbers refer to hours after the start of the IV infusion.
- (iii) The timings of safety, PK, and PD sampling are given as targets to be achieved within reasonable limits. Modifications may be made to the time points based upon the safety and PK information obtained. The scheduled time points may be subject to minor alterations; however, the actual time must be correctly recorded in the CRF. Failure to obtain samples due to clinical issues, such as problems with venous access, will not be considered a protocol violation.
- (iv) Order of assessments should be as follows: ECGs, vital signs (after appropriate rest), PK (when applicable).
 - a All patients will be dosed for 25 weeks (Visits 3 to 13), after which they will be given the option to continue the treatment up to 49 weeks (Visits 14 to 19); the follow-up visits (Visits 20 to 24) for all patients will be conducted accordingly relative to their first dose.

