5.1.3. Treatment Phase

Each cohort will consist of 8 patients randomised (6 LY3303560: 2 placebo) to a 25-week MAD treatment period (7 doses), after which they will be given the option of continuing the treatment up to 49 weeks (up to 6 further doses, Visits 14 to 19). Patients who have completed at least the 25-week treatment period will be followed up for 16 weeks after completion of dosing (Visits 20 to 24) as per the Schedule of Activities in Section 2.

Safety and PK will be assessed throughout the study for each cohort.

Safety will be monitored by AEs, ECGs, vital signs (blood pressure and pulse rate), MRIs, neurological examinations, Columbia Suicide Severity Rating Scale (C-SSRS), and safety laboratory tests. In addition, blood samples for the assessment of immunogenicity will be taken at regular intervals throughout the dosing and follow-up periods. Each patient will have 1 screening (baseline) MRI prior to dosing with LY3303560, another after approximately 4 weeks, and then at approximately 12-week intervals thereafter as specified in the Schedule of Activities (Section 2), for the assessment of any potential imaging abnormalities. Tau imaging using flortaucipir F 18, cognitive and functional assessments (Neuropsychological Test Battery [NTB], the 14-item Alzheimer's Disease Assessment Scale – Cognition [ADAS-Cog₁₄], Mini-Mental State Examination [MMSE], digital clock drawing test [dCDT], and 24-question Alzheimer's Disease Cooperative Study/Activities of Daily Living scale adapted for MCI patients [ADCS-MCI-ADL24]), and cerebrospinal fluid (CSF) (via single lumbar puncture) will be assessed/obtained as detailed in the Schedule of Activities in Section 2. If scheduled on the same day, the cognitive/functional testing should be conducted before the lumbar puncture (LP), and the LP should occur no closer than 24 hours before dosing. The patient must be free from any

post-LP headache for at least 12 hours before dosing. If the LP is performed on a separate day before the cognitive testing, the cognitive/functional testing should be performed at least 24 hours after the LP, and the patient must be free from any post-LP headache for at least 12 hours before dosing (see Section 9.5.1 for detail on CSF sampling).

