10.3.1. Safety Analyses

10.3.1.1. Clinical Evaluation of Safety

All IMP and protocol procedure AEs will be listed, and if the frequency of events allows, safety data will be summarised using descriptive methodology.

The incidence of symptoms for each treatment will be presented by severity and by association with IMP as perceived by the investigator. Symptoms reported to occur prior to randomisation will be distinguished from those reported as new or increased in severity during the study. Each symptom will be classified by the most suitable term from the medical regulatory dictionary.

The number of IMP-related SAEs will be reported.

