| TEAE | Treatment-emergent adverse event: Any untoward medical occurrence that emerges during a defined treatment period, having been absent pretreatment, or worsens relative to the pretreatment state, and does not necessarily have to have a causal relationship with this treatment |
| TPO | third-party organisation |

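### SAP 5.4.1 separates adverse events at randomisation rather than at first infusion, and no final AE summary is tied to the 16-week primary objective (minor)

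*SAP*

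**What the plan says.** The primary endpoint is TEAEs, and the primary objective concerns safety and tolerability after 16 weeks of multiple dosing (Protocol 4, SAP 3).

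**Where the line is drawn.** SAP 5.4.1 states: "Symptoms reported to occur prior to randomization will be distinguished from those reported as new or increased in severity during the study". Protocol 10.3.1.1 has the same sentence. Neither mentions the first infusion.

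**What a TEAE is.** Protocol Appendix 1 defines it as an event that "emerges during a defined treatment period, having been absent pretreatment", or that worsens relative to the pretreatment state. No start day is given. SAP 3 and SAP 5.8 use the term without pointing to that definition, and SAP 5.4.1 does not use it at all.

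**When treatment begins.** The heading of Protocol 2.2 applies the treatment-period label to Visits 2 to 19, which includes the randomisation visit. Protocol 2.3, footnote a, ties it to dosing: "All patients will be dosed for 25 weeks (Visits 3 to 13), after which they will be given the option to continue". Protocol 5.1.3 likewise describes the 25-week treatment period by its 7 doses.

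**The 16-week point.** Protocol 10.3.6 equates 16 weeks with Day 113, four weeks after dose 4. Protocol 5.4 describes the primary objective as safety at steady state and gives Day 113 as the minimum data horizon. The only 16-week look at safety is the per-cohort interim review (Protocol 10.3.6; SAP 4 and 5.7.4.1). SAP 5.7.4 allows such reviews to change without a SAP amendment.

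**The concern.** Two programmers could class the same event differently. One follows SAP 5.4.1 and counts an event between randomisation and first dose as new during the study. The other follows Appendix 1 and treats it as pretreatment. The protocol's two uses of the treatment-period label do not settle the matter.

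The interval is not empty of procedures. The baseline lumbar puncture belongs to Visit 2, and footnote i to Protocol 2.2 foresees a complication before dosing: "Dosing may not proceed until patient has been at least 12 hours free of symptoms of post-LP headache, if present". The order of puncture and randomisation within Visit 2 is not stated, so this example applies only where the puncture comes second.

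The secondary issue is that the final report has no AE summary defined by the time frame in its own primary objective. Incidence over the whole study pools patients followed for quite different lengths of time. SAP 5.3.4 only lists dosing, so no planned summary allows for this.

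**Working it through.** **1. The plan's own figure.** Day 113 reproduces: 1 + 16 × 7 = 113, and dose 4 on Day 85 + 28 = 113. Day 113 is also the day of dose 5 (Visit 11), so four doses precede it.

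**2. Gap between randomisation and first infusion.** Inputs from Protocol 2.2: Visit 2 at Day -8 ± 7; Visit 3 at Day 1.
- Range of Visit 2: Day -15 to Day -1.
- Days before Day 1 with no Day 0: nominal 8, range 1 to 15.
- If a Day 0 is counted: nominal 9, range 2 to 16.

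These figures assume that randomisation falls on the Visit 2 date. Visit 2 tests may be spread over 3 to 5 visit days (Protocol 5.1.1), and the randomisation day within them is not given.

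**3. Effect of one patient whose only event lies in the gap.** The change in incidence is 1/n.

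| Group | n | Change (points) |
|---|---|---|
| One dose, planned size (Protocol 5.2) | 6 | 16.7 |
| 70 mg, as reported (Protocol 3.3) | 7 | 14.3 |
| Placebo pooled, 2 + 2 | 4 | 25.0 |

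The documents give no rate of events in the gap. If the per-patient probability is assumed to be 5%, 10%, 20% or 30%, the expected number with an event is n × p: 0.6, 1.2, 2.4 or 3.6 of 12 active patients, and 0.2, 0.4, 0.8 or 1.2 of 4 on placebo. A patient who also has an event after dosing does not change overall incidence, so these are upper figures for that measure.

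**4. Unequal follow-up.** Inputs: last visit on Day 287 or Day 449 (Protocol 2.3); 7 or 13 doses (Protocol 2.2).

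| | 25-week course | 49-week course |
|---|---|---|
| Days from first dose to last visit | 287 - 1 = 286 | 449 - 1 = 448 |
| Share of days up to Day 113 | 112/286 = 39% | 112/448 = 25% |
| Days after Day 113 | 286 - 112 = 174 | 448 - 112 = 336 |
| Doses before Day 113 | 4/7 = 57% | 4/13 = 31% |

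For scale only, assume a constant hazard, so that incidence over w days is 1 - (1 - p)^(w/112), with p the 16-week incidence. Then p = 10% becomes 24% by Day 287 or 34% by Day 449, and p = 20% becomes 43% or 59%. A whole-study figure is therefore not a substitute for a 16-week one.

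**5. Which side of Day 113 holds the steady-state period.** Protocol 3.2.1.1 gives a half-life of 2 to 3 weeks. With linear one-compartment kinetics and doses every 28 days, the fraction of steady state reached just before dose 5 is 1 - 2^(-112/14) = 99.6% or 1 - 2^(-112/21) = 97.5%. That agrees with Protocol 5.4, which expects steady state after four doses. It also means that the time before Day 113 is mainly the run-up to steady state.

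**The case against.** **TEAE is defined.** A reader might infer that the primary endpoint is undefined or wrong. The documents do not support that: Appendix 1 gives a definition, and the SAP need not repeat it. What stands is narrower. The definition has no start day, and the one explicit onset rule in the AE section uses a different reference point.

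**Gap events are captured and partly identifiable.** The schedule marks no AE review at Visit 2, which might suggest that they are lost. However, Protocol 9.2.1 records AEs from consent, and AE review is scheduled again at Visit 3. SAP 5.4.1 also lists procedure AEs and reports association with study drug, and Protocol 9.2 has the investigator judge relatedness to procedures. A post-puncture headache could therefore be recognised in the listings. This mitigates the problem, but does not fix the class into which the event is counted.

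**A 16-week review is planned.** It might be dismissed as resting on draft data. That reading fails: the draft-data wording in SAP 5.7.4.1 concerns what is loaded into Spotfire, and AEs are reviewed outside it. The review remains interim and changeable, and is not a final table. The synopsis's general promise of summaries by cohort and visit does not define a cumulative TEAE summary either.

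**A cut at Day 113 is not the only reading.** Because Protocol 5.4 speaks of safety at steady state, the 16-week phrase may mean from Day 113 onward. This objection stands in full: a single table stopping before dose 5 would serve only one reading.

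**Conclusion.** The point holds, and it is minor. The randomisation split conflicts with the Appendix 1 definition for events before first dose, and the protocol is inconsistent about when the treatment period starts. The likely result is a small amount of non-drug noise. The 1/n figures show how far one patient can move a percentage; they are not a forecast, since no event rate is given.

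A reader might infer bias between arms. The documents do not support this. Events before any study drug can occur in every arm, patients and investigators are blinded, and nothing suggests that uptake of the extension will differ by arm. No hypothesis tests are planned, so no error rate is affected.

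The secondary point also holds as a gap in reporting: no final AE summary is tied to the 16-week objective, and planned follow-up differs (286 against 448 days). Which side of Day 113 the objective refers to is left open by the documents.

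The day counts assume randomisation on the Visit 2 date and no Day 0. The incidence illustration assumes a constant hazard.

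**What to change.** **Anchor.** In SAP 5.4.1, replace the reference to randomisation with the start of the first infusion (Day 1), and state that TEAEs under Protocol Appendix 1 run from that time. List events between randomisation and first dose separately as pre-treatment. Align Protocol 10.3.1.1 at the next amendment.

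**16-week objective.** State whether it means events up to Day 113 or safety at steady state from Day 113 onward. Present final TEAE incidence by dose and pooled placebo in two periods, first infusion to before dose 5 and Day 113 onward, beside the whole-study table. Use Day 113 as the boundary for patients not given dose 5.

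**Cost.** A wording change, one short listing and one extra table, all from data already collected. SAP 5.1 lets a changed analysis be described in the study report without a protocol amendment. The drawback is sparse cells: the first period omits 3 of 7 or 9 of 13 doses, so the split must be read together with the whole-study table.

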#### **5.4.2. Safety MRI**

Shift tables will be constructed for each dose group to assess the incidence of and changes in vasogenic oedema and microhaemorrhage counts pre- and post-dose (by time) based on MRI.

#### **5.4.3. Evaluation of Immunogenicity**

Antibody formation will be listed and summarized as well as presented graphically over time by patient and treatment. Exposure and antibody formulation may also be explored graphically. If a neutralization assay is performed, the frequency of neutralizing antibodies will be determined. The relationship between the presence (or absence) of antidrug antibodies and clinical parameters (e.g., infusion reaction AEs) may be assessed. Likewise, the relationship between the presence of antidrug antibodies and the PK parameters and PD response to LY3303560 may be assessed.

